9. RESEARCH HYPOTHESIS

Hypothesis 1- Effectiveness: DD+ is effective for improving QoL in patients with co-existing physical (Diabetes or HBP) and mental (depression, anxiety or alcohol misuse) NCD.

Hypothesis 2- Implementation: DD+ is potentially implementable in the Colombian health care system in the context of Amazonas, Guaviare, Cauca and Bogotá D.C for improving QoL in patients with co-occurring physical (Diabetes or HBP) and mental (depression, anxiety or alcohol misuse) NCD.

10. STUDY DESIGN

10.1. General Design

To assess the effectiveness and implementation context of DD+, we will conduct a Hybrid I Randomised Controlled Trial (RCT) using a mixed-methods approach (11,12,40). A health economic analysis will also be included to evaluate the cost of delivering the intervention in the local setting. Effectiveness will be assessed through an RCT, implementation will be evaluated through a descriptive mixed-methods implementation study, and cost-effectiveness will be assessed through an embedded health economic analysis.

Patients in selected HC (Health Centres) will be pre-screened for chronic physical and mental health conditions. Those who meet the initial criteria will be recruited. After accepting to participate and signing informed consent, they will undergo full screening for physical and mental health conditions and QoL. Patients with co-existing physical and mental NCD will be randomised to the active intervention or the control group. Healthcare practitioners (contracted research study professional/staff) trained in DD+ will deliver the assigned intervention to each active intervention participant once per month for six months. Participants allocated to the control group will continue their usual or routine care as established by the HC professionals and procedures. Participants in the control group will be contacted periodically by phone (**Figure 1**).

[figure not shown]
Participants in both study arms will be assessed for outcome measures at baseline, 6, and 12 months. **Table 2** displays the timing and content of study procedures, including interventions, assessments, and interviews across all study visits.

To assess the **implementation context**, a mixed-methods approach will be used, with the following steps:

- a) At the 6-month assessment, all patients in the intervention arm will complete the AIM and IAM scales.
- b) At the 6-month assessment, a subsample of the intervention group participants will be invited to individual interviews to enhance explanatory power and to assess additional implementation criteria, including fidelity, adoption, and feasibility.
- c) During the trial recruitment period, FIM, IAM, and AIM scales will be administered to clinical and managerial leaders from each health centre and to the staff responsible for delivering the intervention. These data will be complemented with semi-structured interviews to enhance explanatory power and to assess additional implementation criteria, including fidelity and adoption.
- d) After the 6-month assessment, clinical and managerial leaders, as well as the staff responsible for delivering the intervention, will again complete the FIM, IAM, and AIM scales, together with a complementary semi-structured interview.

Methods and procedures for the effectiveness assessment are presented in the following sections. Details on the implementation context assessment are provided later in Section 13. **IMPLEMENTATION CONTEXT ASSESSMENT**. The full set of procedures for patients is described in the effectiveness section as an integral guide to study activities, in order to avoid mistakes or confusion during data collection.

Figure 1. Study Phases Overview

Abbreviations: AIM= Acceptability of Intervention Measure; IAM= Intervention Appropriateness Measure; FIM= Feasibility Intervention Measure, Int= Intervention Dynamic DIALOG+(DD+).

v2.0-30 November 2025 BOND+ TRIAL T1_CO_PROTOCOL_Ethics_20251024_v2.0_Control_EN

Table 2. Summary of study visits procedures for patients

| Month | | | M1 | M2 | M3 | M4 | M5 | M6 | M6 | M9 | M12 | M12 | |
|---------------------------------------|---|------------|-----------|----------|-------------|--------------|---------------|--------------|-------------|---------|-----------|--------------|----------|
| Reference date for window calculation | | | Screening | Baseline | Int. I +30D | Int. II +30D | Int. III +30D | Int. IV +30D | Int. V +30D | Int. VI | 6-MA +90D | M.Int I +90D | M.Int II |
| Window (days) | | | +10 | ±10 | ±10 | ±10 | ±10 | ±10 | ±10 | ±15 | ±10 | ±10 | ±10 |
| Study visit name | | Screening* | Baseline* | Int. I | Int. II | Int. III | Int. IV | Int. V | Int VI | 6-MA | M.Int I | M.Int II | 12-MA |
| Study visit number | 0 | 1 | 2 | 3 | 4 | 5 | 6 | 7 | 8 | 9 | 10 | 11 | 12 |
| Invitation | X | | | | | | | | | | | | |
| Informed consent | | X | | | | | | | | | | | |
| MANSA QoL | | X | | | | | | | | X | | | X |
| WHOQOLBREF | | | X | | | | | | | X | | | X |
| EQ5D | | | X | | | | | | | X | | | X |
| Socio-demographics | | | X | | | | | | | | | | |
| PHQ-8 | | X | | | | | | | | X | | | X |
| GAD-7 | | X | | | | | | | | X | | | X |
| AUDIT-C | | X | | | | | | | | X | | | X |
| HbA1 measurement | | X | | | | | | | | X | | | X |
| HBP measurement | | X | | | | | | | | X | | | X |
| Obesity assessment | | X | | | | | | | | X | | | X |
| Eligibility checklist | | X | | | | | | | | | | | |
| SIX | | | X | | | | | | | X | | | X |
| CSRI | | | | X | | | | | | X | | | X |
| AIM | | | | | | | | | | X | | | |
| IAM | | | | | | | | | | X | | | |
| Dialog+** | | | | X | X | X | X | X | X | | X | X | |
| Telephone follow-up¥ | | | | X | X | X | X | X | X | | X | X | |
| Qualitative Interview¶ | | | | | | | | | | X | | | |

Abbreviations: M=Month; D=Day; Int= Intervention DIALOG+; M.Int = Maintenance Intervention DIALOG+; PHQ-8=Patient Health Questionnaire-9; GAD-7=Generalized Anxiety Disorder-7; HBP= High Blood Pressure; SIX=Objective Social Outcomes Index; CSRI= Client Service Receipt Inventory; AIM= Acceptability of Intervention Measure; IAM= Intervention Appropriateness Measure; FIM= Feasibility Intervention Measure; 6-MA: six months assessment.

*The screening visit and baseline visit may be performed on the same day or on a different day.

**Intervention arm only

¥Control arm only

¶A sample of 24 patients allocated to the intervention group will be interviewed. The window for qualitative interviews can be extended by 15 additional days beyond the indicated timeframe.

10.2. Setting

The study will be conducted and participants recruited in primary health care centres, outpatient psychiatric facilities or outpatient services from hospitals in Bogotá, San José del Guaviare (Guaviare), Boquerón (Guaviare), Leticia (Amazonas), Cali (Valle del Cauca), Toribio-Tacueyó (Norte del Cauca) and Santander de Quilichao (Norte del Cauca) in Colombia. The HCs to be included may be either a rural or urban HC. As part of previous work, the NIHR Latam research centre has been working with the community, building trust and collaborating on research.

Recruiting, screening, intervention provision and continuing care will happen at each site.

11. PARTICIPANTS

11.1. Reference Population

Reference population: patients receiving outpatient care for chronic NCDs and mental health conditions in Colombia.

11.2. Study Population

Study population: patients receiving outpatient care at primary care centres or mental health care outpatient facilities with a diagnosis of diabetes, HBP or obesity and at least one mental health condition, such as anxiety, depression or hazardous alcohol consumption in selected health centres in Bogotá, Guaviare, Cauca, and Norte del Cauca.

11.3. Eligibility criteria

Patients with a clinical diagnosis of at least one long-term chronic NCD of interest (diabetes, high blood pressure, or obesity) and at least one mental health condition of interest (anxiety, depression or alcohol misuse) will be eligible to participate.

11.3.1. Inclusion criteria

- Male or female, aged between 18 and 65 at the time of the screening visit;
- Meet either of the following condition combinations:
 - a. Diagnosis of at least one long-term physical chronic non-communicable disease of interest (diabetes, high blood pressure, or obesity) **and** positive screening of at

least one mental health condition of interest (anxiety, depression or hazardous alcohol consumption). **Table 3** displays the positive screening criteria.

- b. Diagnosis of at least one mental health condition of interest (anxiety, depression or hazardous alcohol consumption) **and** a positive screening of at least one long-term chronic NCD of interest (diabetes, high blood pressure, or obesity). **Table 3** displays the positive screening criteria.
- c. Diagnosis of at least one mental health condition of interest (anxiety, depression or hazardous alcohol consumption) **and** one long-term physical chronic non-communicable disease of interest (diabetes, high blood pressure, or obesity).
 - currently receiving outpatient care for physical or mental NCD at one of the study sites;
 - have a low quality of life score as measured by MANSA of ≤ 5
 - speak and understand Spanish;
 - have legal residency status in Colombia.

11.3.2. Exclusion criteria

- Diagnosis of dementia, or
- clinical diagnosis of schizophrenia or other psychotic disorders, or
- an inpatient at the time of recruitment, irrespective of the cause, or
- absence of health insurance, or
- inactive health insurance at the moment of recruitment

Table 3 .Positive Screening Criteria

| Condition | Screening Tool / Measure | Positive Screening Definition |
|---|--|---|
| Depression | PHQ-8 | Score ≥ 10 (41) |
| Anxiety | GAD-7 | Score ≥ 10 (41) |
| Alcohol Use (Hazardous alcohol consumption) | AUDIT-C | Score ≥ 4 in men OR ≥ 3 in women (42) |
| Prediabetes/Diabetes | Glycated haemoglobin (HbA1c) | $\geq 5.7\%$ (prediabetes level or above) (43) |
| Obesity | BMI / Abdominal circumference | BMI ≥ 30 OR ≥ 91 cm in men OR > 89 cm in women (44) |
| Hypertension | Blood pressure (average of 3 readings, ≥ 5 min apart) | Systolic ≥ 130 mmHg and/or Diastolic ≥ 80 mmHg (45) |

12. PROTOCOL PROCEDURES

Itemised list of procedures for DIALOG+/DD+ RCT patient participants

- Identify sites where RCT will take place
- Identify and invite to participate in a roll-in basis patients across all sites
- Potentially eligible patients sign the consent form
- Potentially eligible participants complete MANSA with the researcher. Those scoring less or equal to 5 go on to complete the full baseline assessment.

- Potentially eligible participants complete physical and mental NCDs screening.
- Researcher confirms the inclusion criteria
- Researcher completes the baseline assessment with participants
- Randomise participants to either the intervention group or the control group (standard care)
- Patients continue to receive treatment as usual. Those in the intervention arm will complete DIALOG+/DD+ once a month for 6 months.
- Researchers complete a 6-month follow-up assessment with patients
- A purposive sample of 24 intervention patients will be contacted for an individual semi-structured interview
- Conduct face-to-face individual interviews with 24 participants.
- Researchers complete a 12-month follow-up assessment

12.3. Recruitment

Recruitment centres will correspond to each study site (health centres). Participants will be recruited through one of the following mechanisms:

- Waiting room invitation: Local research staff will approach eligible patients in the waiting area, provide the study information sheet, and offer a screening visit. This visit can be scheduled for the following day or performed that same day, depending on the capacity of the HC and the local research team.
- Practitioner referral: HC practitioners will be briefed on the study and may invite eligible patients during routine consultations. Interested patients may authorise the research team to contact them to provide further details and schedule a screening visit.
- Study advertisements: Visual materials will be displayed in health centres with contact details for interested patients. Patients may contact the research team to join the study.

Upon acceptance, potential participants will meet individually with a researcher to sign the consent form and complete the eligibility screening.

12.4. Informed Consent

Individuals who respond to the study information with interest will be contacted and invited by phone or letter to attend a face-to-face meeting with a researcher. Researchers will review information sheets with interested individuals and take the time to address any questions or concerns that are raised. At this stage, contact details will be confirmed and availability ascertained for attendance at intervention sessions, interviews, or appointments.

All participants will be asked to provide informed consent at the enrolment visit by signing and dating an informed consent form prior to any data collection commencing. The form will contain the exact nature of the study, what it will involve for the participant, the implications and constraints of the protocol, the

known side effects and any risks involved in taking part. It will be clearly stated that the participant is free to withdraw from the study at any time for any reason without prejudice to future care, without affecting their legal rights, and with no obligation to give the reason for withdrawal.

If signed on paper, the participant will retain one copy of the informed consent form, and the research team will keep the other, storing it in a locked filing cabinet and uploading a copy to the participant's records in the REDCap secure system (Research Electronic Data Capture). If electronically signed, the participant should receive a copy of the signed consent form on their phone or by email. If there is no available electronic source to deliver the copy, the researcher responsible for obtaining informed consent must provide a physical copy of the signed form to the participant.

All local researchers authorised to obtain informed consent will receive training based on Good Clinical Practice. Researchers must be suitably qualified with proven knowledge of current local and international clinical research regulations.

The researchers will assess each patient's level of understanding during the recruitment and consent process, alongside discussion with patients' clinicians where necessary. If there are any doubts regarding the patient's capacity to consent to take part in research, this will need to be resolved before proceeding with study participation. If any doubts about their capacity emerge during the recruitment process, or capacity to consent appears to change during their participation in the study, their capacity to consent will be re-evaluated before continuing with study participation.

12.5. Screening and Eligibility Assessment

[figure not shown]
Participants must have at least one long-term chronic non-communicable disease (NCD) of interest, such as diabetes, high blood pressure or obesity, and at least one mental health condition, including anxiety, depression, or hazardous alcohol consumption. Consequently, a screening phase is necessary to thoroughly assess the inclusion criteria. Participants can be recruited from specialised mental health centres or primary health centres focused on physical non-communicable diseases.

To complete the eligibility assessment, patients will complete the MANSA, where only individuals with a MANSA score of ≤ 5 points will be eligible to continue with the study.

After QoL assessment, all participants under the MANSA threshold will be screened for mental health conditions with PHQ-8, GAD-7 and AUDIT-C scores irrespective of a previous mental health diagnosis. Afterwards, all participants will be screened for diabetes, HBP, and obesity. Diabetes screening will be based on HbA1 measurement or a previous confirmed diagnosis when the patient is under treatment. HBP will be based on double standard measurement at the screening visit or a previous confirmed diagnosis by the healthcare provider. Obesity will be evaluated using the abdominal circumference measurement at the screening visit.

Error! Reference source not found. presents a flow diagram that summarises the process from recruitment up to randomisation for each participant.

Figure 2. Participant selection and enrolment flow diagram

12.6. Baseline Assessment

[figure not shown]
Measurements performed for screening and eligibility assessment will be part of the Baseline Assessment. Additionally, participants will complete a socio-demographic questionnaire with the help of a researcher. The researcher will administer the following scales to patients (See **Table 2**):

- Objective Social Outcomes Index (SIX)
- Socio-demographic questionnaire
- EQ5D
- WHOQOL-BREF
- CSRI

12.7. Randomisation

The unit of randomisation will be the individual participant. Site-stratified blocked randomisation, with a variable block size ranging from two to four, will be performed on a rolling basis during the recruitment period. A randomisation schedule will be defined for each health centre (study site). Within each stratum, participants will be randomised in a 1:1 ratio to either DD+ or the control group. Randomisation will be performed using REDCap or via a phone call, following the corresponding randomisation schedule.

Figure 3. Study Randomisation Summary

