12.8. Blinding and code-breaking

Due to the nature of the DD+ intervention and the usual care control group, patients cannot be blinded to the intervention. Researchers responsible for recruitment, screening, baseline assessment, and scheduling intervention appointments will be unblinded. Researchers conducting outcome evaluations will be blinded to participant allocation, and participants will be instructed not to disclose details of their allocation to the research team at any time during the study.

Blinded statisticians will perform statistical analysis. Qualitative interviews and analysis will be conducted by unblinded researchers.

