16. STUDY LIMITATIONS AND BIAS CONTROL

Due to the diversity of settings in terms of geographic location and sociodemographic characteristics, the risk of bias due to lack of representativeness of the Colombian population will be low. The randomisation procedure is also expected to generate balanced groups, reducing the risk of differential selection bias and minimising the chances of differential losses. However, since participants in the control group will have less contact with the study team and will be aware of their allocation due to unblinding, there is a risk of higher losses in this group. To mitigate this, routine phone calls will be made to control participants as reminders for the 6- and 12-month follow-up assessments.

A risk of contamination bias exists due to the public availability of the DIALOG+ application in the Play Store. However, for the active group, the intervention will be delivered by a trial clinician in the intervention appointments. In contrast, the follow-up visits for the control group will be through brief phone calls. Neither the trial clinician nor the researcher in charge of the follow-up call will be part of the patient care team. Furthermore, the fact that the application is publicly available will not be explicitly disclosed to participants to minimise the risk of bias.

The lack of blinding may also introduce bias through QoL outcome overestimation. However, outcome assessors and statisticians will remain blinded to allocation to reduce the risk of overestimating the effect or its magnitude. The risk of allocation concealment failure exists, but it is limited because the allocation will be automatically provided by the REDCap platform and only disclosed at the end of the baseline assessment visit.

A risk of outcome misclassification also exists. Although the diagnostic scales and tests used are validated and widely applied, the absence of measurement errors cannot be guaranteed. However, any misclassification is not expected to be differential. Finally, the risk of confounding is low due to randomisation, but not negligible. Therefore, statistical analyses for primary and secondary outcomes will adjust for relevant covariates, and the interpretation of results will consider the distribution of known variables among intervention and control groups.

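### Stated block sizes of two to four per health centre, with unblinded recruiters, seriously weaken allocation concealment, and the defence in Section 16 does not address prediction

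*Protocol*

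**What the plan says.** Section 12.7 of the protocol sets the method: "Site-stratified blocked randomisation, with a variable block size ranging from two to four, will be performed on a rolling basis during the recruitment period". Each health centre has its own schedule, and "Within each stratum, participants will be randomised in a 1:1 ratio to either DD+ or the control group". On how an allocation is obtained, the same section says: "Randomisation will be performed using REDCap or via a phone call, following the corresponding randomisation schedule".

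Section 12.8 states that "Researchers responsible for recruitment, screening, baseline assessment, and scheduling intervention appointments will be unblinded" and that "patients cannot be blinded to the intervention". Outcome assessors are to be blinded.

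Section 12.3 lists three recruitment routes: approach in the waiting room by local research staff, referral by a practitioner, and advertisements. Under Section 12.10, the participant completes the entry MANSA (5 or less) with the researcher's help at Visit 1. Screening and baseline may fall on the same day or up to ten calendar days apart, and Visit 2 ends with randomisation.

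Section 16 concedes a concealment risk but discounts it: "The risk of allocation concealment failure exists, but it is limited because the allocation will be automatically provided by the REDCap platform". It adds that the allocation is disclosed only once the baseline visit is over.

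**The concern.** Concealment can fail in two ways. The current allocation may be seen before the participant is committed, or it may be predicted from those already made. Release through REDCap after baseline protects against the first. It does nothing about the second, which depends on block size, on the stratum within which blocks run, and on who knows the earlier allocations.

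Here all three point the wrong way. The blocks are very small and their sizes are stated in the protocol. They run within single centres. The people who enrol patients are unblinded, and whoever books DD+ appointments must know which participants were allocated to DD+. Some of these staff choose whom to approach, can influence when screening is booked, and help with the MANSA that decides entry and serves as the baseline covariate.

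A recruiter with a good idea of the next arm could, without intending to, direct more motivated patients, or those better able to attend monthly, towards DD+. The primary outcome is the unblinded participant's own rating. Adjustment for baseline MANSA would not remove selection on motivation or ability to attend. Once participants are enrolled, the problem cannot be repaired.

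**Working it through.** **Inputs from the protocol.** Blocks of two to four, 1:1, one schedule per centre (12.7); 226 participants (15.2); 15 centres (15.11.4), or the seven locations named in 10.2 as a sensitivity case. That gives 226/15 ≈ 15 per centre or 226/7 ≈ 32 per location. The protocol states no figure for predictability. Its sample size does reproduce: with SD 0.9, correlation 0.4 and difference 0.4, an analysis adjusted for baseline needs 90 per group (power 90.2%), and 90/0.8 = 112.5, rounded up to 113. This point does not alter it.

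**Assumptions not in the protocol.** Sizes 2 and 4 equally likely; equal recruitment across centres; the guesser knows all earlier allocations at the centre; nobody else is randomised there between guess and allocation. A block of 3 cannot be balanced 1:1, so only 2 and 4 remain.

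**Strategy.** Name the arm that is behind at the centre; toss a coin when the arms are level.

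**By hand, for complete blocks (T = DD+, C = control):**
- Block of 2: 0.5 + 1 = 1.5 correct of 2. One position has unequal arms, and the guess there is always right.
- Block of 4, six equally likely orders. Two are of type TTCC: 0.5 + 0 + 1 + 1 = 2.5 correct, three unequal positions, two guessed right. Four are of type TCTC or TCCT: 0.5 + 1 + 0.5 + 1 = 3 correct, two unequal positions, both guessed right. Mean correct = (2×2.5 + 4×3)/6 = 2.83 of 4. Mean unequal positions = (2×3 + 4×2)/6 = 2.33, of which 2 are guessed right.
- One block of each size, six positions: correct = (1.5 + 2.83)/6 = 72%; unequal = (1 + 2.33)/6 = 56%; right when unequal = (1 + 2)/(1 + 2.33) = 90%.
- Certain: once one arm is two ahead, the block must be a 4 and its last two places are fixed. This happens in one third of 4-blocks, so (1/3 × 2)/6 = 11%.

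**Simulation, allowing for incomplete last blocks:**

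| Blocks | Correct, 15 centres | Correct, 7 locations | Certain, 15 centres | Certain, 7 locations |
|---|---|---|---|---|
| 2 only | 73.5% | 74.8% | 47% | 50% |
| 4 only | 69.1% | 70.6% | 29% | 33% |
| 2 and 4 | 70.7% | 71.9% | 10% | 11% |
| 4 and 6 | 67.5% | 68.8% | 6% | 6% |
| 4, 6 and 8 | 66.3% | 67.4% | 2% | 2% |

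Simple randomisation gives 50%. With 2 and 4 over 15 centres, about 52% of allocations are made while the arms are unequal, and the lagging arm is then right about 90% of the time. The other 48% stay a coin toss. With 4, 6 and 8, accuracy in unequal states falls to about 77%. In numbers, 10% of 226 is about 23 certain allocations and 2% is about 5.

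**If one other participant at the centre is randomised between guess and allocation** (15 per centre), accuracy falls to about 55% with 2 and 4, and is about 59% with 4, 6 and 8.

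**Imbalance.** The mean absolute difference between arms within a centre is 1.00 (2 and 4) against about 1.1 (4, 6 and 8) at 15 per centre, and 0.22 against about 0.55 at 32.

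**Bias, hypothetical only.** If recruiters shifted prognosis by s MANSA points towards each guessed arm at every allocation, bias = 2 × s × (2P − 1), where P is the share guessed correctly. With P = 0.707 this is 0.83 × s: zero if s = 0, and 0.075 if s = 0.09 (0.1 SD). With P = 0.663 it is 0.33 × 2 × 0.09 = 0.059. The protocol gives no value for s.

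**The case against.** The strongest objection concerns timing. The 71% applies at the moment of randomisation, whereas steering would happen when a patient is approached or booked. Consent, the MANSA threshold, condition screening and up to ten days lie between. Recruitment is rolling, and one intervening randomisation takes the guess most of the way back to chance. Larger blocks are then slightly worse (59% against 55%). This stands as a real limit. It does not remove the point, because Section 12.10 allows screening and baseline on the same day, and at about 15 participants per centre an intervening randomisation will often not occur.

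A reader might infer that recruiters see every earlier allocation at their centre. The protocol does not say so. It says they are unblinded, gives no number of recruiters per centre, and has the local research coordinator facilitate appointments (12.10). Knowledge of earlier allocations is likely, and nothing in the protocol restricts it, but it remains an inference. Two of the three recruitment routes also do not rely on a recruiter choosing whom to approach.

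A reader might also take the phone route in Section 12.7 to contradict Section 16. It does not. A call to a central holder of the schedule fits the text. Section 16 simply leaves that route out when it relies on REDCap.

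Finally, naming the lagging arm needs no knowledge of block sizes, so withholding the sizes reduces only the certain predictions. That is correct, and is why the fix should not rest on block size alone.

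**Conclusion.** The concern holds in this form: small stated blocks within each centre, combined with unblinded recruiters, seriously weaken concealment, and Section 16 answers a different risk. An informed recruiter would be right about 71% of the time (69 to 75% across the possible mixes of 2 and 4 and both numbers of centres), about 90% when the arms are unequal under the equal mix, and certain for about 10%. The certain share could reach about 50% if every block were a 2. All of this rests on knowledge of earlier allocations and no intervening randomisation.

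It would go too far to say that concealment is defeated. Nearly half of allocations stay 50/50 under the equal mix, and the current allocation is still released only after baseline. Nor do the documents support a stated bias in the primary estimate. A figure such as 0.075 points against the 0.4-point target depends wholly on an assumed amount of steering, applied at every allocation, and ignores whatever part baseline adjustment would absorb. The weakness should be corrected before recruitment because doing so costs little and cannot be done afterwards.

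**What to change.** Before the first participant is randomised:

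1. Use randomly mixed larger even blocks, for example 4 and 6, or 4, 6 and 8.
2. Remove the sizes from the protocol and leave them only with the person who builds the REDCap list.
3. State in Section 12.7 that any phone allocation is released by a central holder, one at a time, after Visit 2 data are saved.
4. Where existing staffing allows, keep those who approach and screen patients from seeing the centre's running allocation list. This addresses the cause more directly than block size does.
5. Amend Section 16 to acknowledge prediction from earlier allocations and to cover the phone route.

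The cost is a revised paragraph in each section and a new REDCap allocation table. Sample size is unaffected. Within-centre imbalance rises slightly (about 1.0 to 1.1 participants at 15 per centre, 0.2 to 0.55 at 32). The gain in overall guessing is modest: from 71–72% to 66–67% with 4, 6 and 8, or to 68–69% with 4 and 6. The main benefit is in certain predictions, which fall from about 10% to about 2% with 4, 6 and 8, or to about 6% with 4 and 6.
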